**5. ANALYSIS POPULATIONS**

The study will use the following analysis populations for data summaries.

**Table 11: Analysis Populations**

Population	Definition	Displays
Safety Population	The Safety Population will include all subjects who have at least 1 injection of study medication.	All demographic, baseline characteristics and safety parameters will be summarized based on this population.
Evaluable Population	The Evaluable Population will include all subjects in the Safety Population who have completed screening procedures and at least 1 post baseline assessment of the Likert Scale score of aesthetic appearance improvement.	All efficacy analysis will be based on this population.

**6. STATISTICAL METHODS**

**6.1. General Methodology**

All statistical tests, summary tables and data listings will be prepared using SAS version 9.4

All statistical tests of efficacy parameters will be two-sided with a significance level of  $\alpha=0.05$ , unless specified otherwise. Statistical tests will be supported by presenting estimates and 95% confidence intervals (CI) for the respective treatment effects. These estimates and CI will be based on the linear regression model.

Continuous data will be summarized using descriptive statistics. Discrete data will be summarized using frequency counts and percentages. The denominator will be based on the number of subjects in the appropriate population.

For the purpose of display, the summary results will be rounded as follows:

- Minimum and maximum: same number of decimal places as the raw data.
- Mean and Median: one more decimal place than the raw data.
- SD: Two more decimal places than the raw data.
- Percentages will be displayed with one decimal place precision. A zero count will be left blank.
- The standard form of a percentage change variable is 0 decimal place.

For categorical variables with missing values, a category documenting the frequency of missing values will be displayed in the summary tables.

Summary tables, subject listings, graphs and any supportive SAS output will include footnotes that will indicate:

- Date of data extraction
- Date and time of output generation
- SAS program name, including the path, that generated the output

When calculating percentages, the denominator will be based on the number of subjects with non-missing values. If the denominator is expected to change over time, then the denominator used to calculate the percentage will be based on the number of subjects with non-missing values at each visit. Any subject removed from an analysis will be noted at the bottom of the table along with the reason the subject was removed.

Empty summary tables will be presented with a note stating that “No Subjects Met Criteria.”

Subject listings of all data from the eCRFs as well as any derived variables will be presented.

## **6.2. Adjustments for Covariates**

Not applicable.

## **6.3. Derived Variables**

[Table 12](#) defines the derived variables for study parameters.

**Table 12: Derived Variables and Definition**

Variable	Definition
Age Group	<35 years 35 – <45 years 45 – <65 years ≥65 years
Height (cm)	If height is recorded in inches, then height is equal to the recorded value multiplied by 2.54 and then rounded to 1 decimal place.
Weight (kg)	If weight is recorded in pounds, then weight is equal to the recorded value multiplied by 0.454 and then rounded to 1 decimal place.
Body Mass Index (BMI)	BMI will be computed using height and body weight measured at screening as, $BMI (kg/m^2) = Weight (kg) / Height (m)^2$
BMI Group	Underweight (<18.5 kg/m  ) Normal Weight (18.5 – <25.0 kg/m  ) Overweight (25.0 – <30.0 kg/m  ) Obese (≥30.0 kg/m  )
Relative Day	The day of first injection of study drug will be considered as relative day 1
Study Day (for assessment on or after Day 1)	Study Day will be computed as, Date of Assessment – Date of Day 1 + 1
Study Day (for assessment before Day 1)	Study Day will be computed as, Date of Assessment – Date of Day 1
Baseline	Baseline is defined as the last non-missing measurement/assessment prior to the first dose of study drug. For vital signs, the baseline will be the Day 1 pre-dose values. For clinical laboratories this could be the screening value, or it could be an unscheduled lab, if the unscheduled lab is the closest value preceding the first injection.
Change from Baseline	Change from baseline will be derived as, post-baseline visit/time point value – the baseline value.
Last Date in Study	
 
• The date of Day 71 if the subject completes the study
 
• The date of early termination visit if the subject is terminated early from study at a non-scheduled visit
 
• The date of the latest scheduled visit if the subject is terminated early from study at a scheduled visit or lost to follow-up.
 

Age at EFP Symptom Onset	Date of EFP symptoms reported – Date of Birth/365.25. See section 6.4.1.3 for handling of partial or unknown EFP symptom onset dates.
Time Since Last EFP Treatment	Date of most recent EFP treatment – Date of informed consent/365.25. See section 6.4.1.3 for handling of partial or unknown EFP treatment dates.
Baseline CR-PCSS Score	Investigator baseline CR-PCSS scores for each treatment area will be based on the investigator's CR-PCSS evaluation done at the Screening visit.
Baseline for Hexsel Depression Depth Scale	The investigator assessment performed at Screening for each treatment area will be considered as Baseline.
Duration of Exposure at Each Visit	Date/Time of Last Injection – Date/Time of First Injection
Duration of AE	AE end date – AE start date + 1
AE Onset Day	AE start date - Date of first injection + 1

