5. SCHEDULE OF EVENTS

	Screening (Day-21 to Day -1)	Day 1	Day 4 (± 1 day)	Day 8 (± 1 day)	Day 15 (± 2 days)	Day 22 (± 2 days)	Day 43 (± 2 days)	End of Study/ Early Termination Day 71 (± 3 days)	Unscheduled Clinic Visit ^a
Procedures									
Informed consent ^b	X								
Inclusion/exclusion criteria review	X	X ^c							
Demographic data	X								
3-D Photography	X	X ^{d,e}	X	X	X	X ^{d,e}	X ^{d,e}	X	
Medical/surgical/EFP history (including previous treatment)	X								
Prior/concomitant medications/procedures	X	X ^c	X	X	X	X	X	X	X
Physical Examination	X							X	X
Height	X								
Weight	X	X ^e						X	X
Fitzpatrick skin type	X								
Vital signs	X	X ^f				X ^f	X ^f	X	X
12-lead ECG	X								
Clinical Laboratory Tests	X							X	X
Anti-AUX-I/anti-AUX-II antibody level sample		X ^e						X	
Serum pregnancy test	X								
Urine pregnancy test		X ^e				X ^e	X ^e	X	X
Assignment of treatment area (buttocks or thighs)	X								

	Screening (Day-21 to Day -1)	Day 1	Day 4 (± 1 day)	Day 8 (± 1 day)	Day 15 (± 2 days)	Day 22 (± 2 days)	Day 43 (± 2 days)	End of Study/ Early Termination Day 71 (± 3 days)	Unscheduled Clinic Visit ^h
Procedures									
Selection of 2 dimples within each treatment area for volumetric assessment	X	X ^e							
CR-PCSS	X								
Hexsel Depression Depth Scale	X					X	X	X	
Assign Treatment Arm (dosing injection technique)		X ^e							
Mark the dimple injection sites		X ^e				X ^e	X ^e		
Study drug administration		X				X	X		
Injection site reactions/local tolerability in the treated areas		X	X	X	X	X	X	X	X
All other adverse events					X				

^aDuring unscheduled visits the investigator or designee may perform any study procedure that they deem clinically necessary (eg, vital signs, clinical laboratory tests, pregnancy test, etc).

^bPerformed prior to any study-required assessments.

^cShould be reassessed and verified prior to study drug administration.

^dComplete before and after marking injection sites.

^eComplete prior to study drug administration.

^fVital signs will be collected up to 4 hours prior to, and at 15 and 30 minutes after study drug administration on Days 1, 22, and 43.

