**Table 1: Schedule of Events (Continued)**

Procedure	Screening (Day-21 to Day -1)	Day 1	Day 4 (± 1 day)	Day 8 (± 1 day)	Day 15 (± 2 days)	Day 22 (± 2 days)	Day 43 (± 2 days)	End of Study/ Early Termination/ Day 71 (± 3 days)	Unscheduled Clinic Visit a
Study drug administration		X				X	X		
Injection site reactions/local tolerability in the treated areas		X	X	X	X	X	X	X	X
All other adverse events	←-----X-----→								

a During unscheduled visits the investigator or designee may perform any study procedure that they deem clinically necessary (eg, vital signs, clinical laboratory assessments, pregnancy test, etc).

b Performed prior to any study-required assessments.

c Should be reassessed and verified prior to study drug administration.

d Complete before and after marking injection sites.

e Complete prior to study drug administration.

f Vital signs will be collected up to 4 hours prior to, and at 15 and 30 minutes after study drug administration on Days 1, 22, and 43.

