### 3.20. Vital Signs

Vital signs measurements will be taken at Screening, Day 1, 22, 43, and at the EOS visit. On treatment visits (Days 1, 22, and 43), vital signs will be assessed at 4 hours prior to, and at 15 and 30 minutes after study drug administration.

Vital signs measurements include: systolic and diastolic blood pressure, respiratory rate, pulse rate, body temperature, height, and body weight.

Height and body weight measurements will be taken at Screening. Body weight will also be measured at Day 1 and at EOS visit.

Any abnormality in vital sign observed, will be considered as an AE or SAE as appropriate.

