**4.6.2.2. Potentially Clinically Important Vital Sign Values**

Vital sign values are PCI if they meet both the observed value criteria and the change from baseline criteria. The PCI vital sign values are presented in Table 10 below.

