**Table 10: Potentially Clinically Important Vital Sign Criteria**

Parameter	PCI Low	PCI High
Systolic Blood Pressure	≤90 mmHg and decrease ≥20 mmHg from baseline	≥180 mmHg and increase ≥20 mmHg from baseline
Diastolic Blood Pressure	≤50 mmHg and decrease ≥15 mmHg from baseline	≥105 mmHg and increase ≥15 mmHg from baseline
Pulse Rate	≤50 bpm and decrease ≥15 bpm from baseline	≥120 bpm and increase ≥15 bpm from baseline
Respiratory Rate	≤8 brpm and decrease ≥7 brpm from baseline	≥25 brpm and increase ≥7 brpm from baseline
Temperature		≥38.3°C and increase ≥1.1°C from baseline

bpm=Beats per minute; brpm=Breaths per minute

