### **7.8.4. Vital Signs**

Vital signs (systolic and diastolic blood pressure, pulse rate, respiratory rate, body temperature, and body weight) will be summarized using descriptive statistics for observed and change from baseline values for all assessments visits.

The PCI vital signs values will be summarized by counts and percentages. Refer to [Table 10](#) for PCI criteria.

A subject listing will be presented for vital signs results.

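### Vital signs at 15 and 30 minutes after the Day 22 and Day 43 injections are compared only with the Day 1 pre-dose value; a same-visit comparison should be added

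*SAP*

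**What the plan says.** **Timing.** The schedules in both documents place vital signs before dosing "and at 15 and 30 minutes after study drug administration on Days 1, 22, and 43". Both allow the pre-dose reading to be taken as much as 4 hours before the injection. SAP 3.20 words this slightly differently ("vital signs will be assessed at 4 hours prior to, and at 15 and 30 minutes after study drug administration"), but it too provides a pre-dose reading at every treatment visit.

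**Reference value.** SAP Table 12 sets one baseline: "For vital signs, the baseline will be the Day 1 pre-dose values". The same table adds: "Change from baseline will be derived as, post-baseline visit/time point value – the baseline value". Every later reading, including those at 15 and 30 minutes on Days 22 and 43, is thus compared with Day 1 pre-dose.

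**PCI rule.** SAP 4.6.2.2 requires two conditions together: "Vital sign values are PCI if they meet both the observed value criteria and the change from baseline criteria". For low systolic pressure, Table 10 gives "≤90 mmHg and decrease ≥20 mmHg from baseline". Diastolic pressure, pulse and respiratory rate follow the same pattern in both directions.

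**Analysis.** SAP 7.8.4 has vital signs "summarized using descriptive statistics for observed and change from baseline values for all assessments visits", plus PCI counts and a subject listing. Protocol 17.6.5 likewise plans changes from baseline by visit. Neither document defines a change from the pre-dose value of the same visit.

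**The concern.** Readings shortly before and shortly after an injection are most informative as a pair. On Day 1 the plan uses that pair, because the baseline is the same-day pre-dose value. On Days 22 and 43 it does not: four of the six post-dose time points are compared with a reading taken weeks earlier, although a same-visit reading is in the database.

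These are the re-exposure doses of what protocol 10.3.6 calls a foreign protein. That section keeps subjects under observation for 30 minutes because of possible immediate immunological events. Protocol 8.1.2 reports more than 90% of CCH-treated subjects seropositive after 3 treatments. The protocol does not state why vital signs are taken at 15 and 30 minutes, so linking them to acute reactions is an inference, though a natural one.

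At stake is the secondary objective, safety by injection technique. SAP 7.8 tabulates safety by arm and region, and the arms are small: 6 subjects per region and 12 overall. One subject classified differently moves a percentage by 1/12 = 8.3 points overall, or 1/6 = 16.7 points within a region.

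**Working it through.** The plan gives no numerical result on this point to reproduce. The check uses the visit days, the Table 10 criteria and constructed readings.

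**1. Age of the reference value.** Day 22 − Day 1 = 21 days (3 weeks). Day 43 − Day 1 = 42 days (6 weeks). With the ±2-day visit windows the intervals are 19 to 23 and 40 to 44 days.

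**2. What the planned change contains.** For a post-dose reading on Day 22 or Day 43:

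post − Day 1 pre = (post − same-visit pre) + (same-visit pre − Day 1 pre)

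The first term is the change across the injection. The second is drift between visits. The planned analysis reports only the sum.

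**3. The PCI rule applied twice.** The readings below are constructed; they are not trial data. The thresholds are those of Table 10.

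| Parameter | Day 1 pre | Same-visit pre | Post | Change from Day 1 | PCI as planned | Same-visit change | PCI on same-visit change |
|---|---|---|---|---|---|---|---|
| Systolic, mmHg | 108 | 122 | 89 | 89 − 108 = −19 | no | 89 − 122 = −33 | low |
| Diastolic, mmHg | 64 | 72 | 50 | 50 − 64 = −14 | no | 50 − 72 = −22 | low |
| Pulse, bpm | 64 | 78 | 50 | 50 − 64 = −14 | no | 50 − 78 = −28 | low |
| Systolic, mmHg | 165 | 150 | 182 | 182 − 165 = +17 | no | 182 − 150 = +32 | high |
| Systolic, mmHg | 125 | 108 | 90 | 90 − 125 = −35 | low | 90 − 108 = −18 | no |

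The first four rows lose a flag because of drift. The last row gains one: the fall across the injection is under 20 mmHg, and the other 17 mmHg was present before dosing.

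**4. Where a reading exactly on the threshold cannot be flagged.** The Day 1 value must differ from the reading by at least the change criterion.

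- Low side: no flag is possible if Day 1 was below 90 + 20 = 110 mmHg systolic, 50 + 15 = 65 mmHg diastolic, or 50 + 15 = 65 bpm, however large the same-day fall.
- High side: no flag is possible if Day 1 was above 180 − 20 = 160 mmHg systolic, 105 − 15 = 90 mmHg diastolic, or 120 − 15 = 105 bpm.

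These limits hold only at the threshold itself. A reading beyond it needs a less stringent Day 1 value: systolic 105 on Day 1 and 85 post-dose is a fall of 20 and is flagged.

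**The case against.** A single baseline before first dose is a legitimate and common choice. It matches the SAP's general definition of baseline, it is consistent with protocol 17.6.5, and it answers a real question: how far a reading lies from the untreated state. Nothing here contradicts the protocol. That stands, and it is why the Day 1 baseline should not be replaced. Replacement would also remove the flag from a series such as 125/108/90, where the post-dose value is at the threshold and 35 mmHg below the untreated value.

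A reader might infer that acute reactions at re-exposure would go unnoticed. The documents do not support this:

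- Protocol 14.9 has the investigator review every vital sign and record clinically significant values as adverse events; SAP 3.20 also treats abnormal vital signs as reportable.
- Protocol 10.3.6 requires stable vital signs before a subject leaves observation.
- Hypersensitivity, including anaphylaxis, is an event of special interest, with its own table and listing under SAP 7.8.2.
- SAP 7.8.4 summarizes observed values and lists all results, so each pair of readings can be seen.

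Nor does any stopping rule or formal test use the PCI count. What survives is narrower: no planned summary isolates the change across the injection on Days 22 and 43, and the PCI counts there answer a different question from those on Day 1.

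The same-visit reference is itself imperfect, since the reading may be as much as 4 hours old. That is still far closer to the injection than 21 or 42 days.

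**Conclusion.** The point holds as a gap in the planned summaries and PCI counts for Days 22 and 43. Day 1 is unaffected. The constructed readings show that classification can go wrong in both directions, and this needs no assumption about variability.

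A reader might want a misclassification rate. The documents give no blood-pressure variability and no expected acute change, so none can be stated. Simulation shows the difficulty. Assume a mean systolic pressure of 118 mmHg, between-subject SD 12, visit-to-visit SD 5 to 12, and an acute fall averaging 25 to 35 mmHg (SD 4) applied to every reading. Then about 2% to 19% of readings that are PCI-low on the same-visit change are missed with the Day 1 baseline. But those inputs also make about 39% to 70% of all readings PCI-low on the same-visit change. The percentages follow from the assumed fall and say little about this trial.

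This is an inexpensive improvement to the secondary safety analysis, not the correction of an error.

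**What to change.** Keep the Day 1 pre-dose baseline for all readings as now planned, and add:

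- **SAP Table 12:** a second derived variable for the 15- and 30-minute readings on Days 22 and 43, defined as the post-dose value minus the last non-missing pre-dose value of the same visit.
- **SAP 4.6.2.2:** a second PCI evaluation of those readings that applies the existing Table 10 criteria, unchanged, to the same-visit change. Report it beside the planned count, not in place of it.
- **SAP 7.8.4:** a descriptive summary of the same-visit change by time point, arm and region, with each table labelled by its reference value.

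SAP 3.20 and the schedule should also describe the timing of the pre-dose reading in the same way, so that the reference is unambiguous.

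The cost is one derived variable, some SAP wording and extra rows or columns in the vital-sign tables. No new data are needed, and neither thresholds nor subject care change. Readers will meet two reference values, and a footnote should say that the same-visit reading may precede the injection by as much as 4 hours.

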#### **4.4. Prior EFP Treatment**

Prior EFP treatment will be obtained from the prior/concomitant medication and/or prior/concomitant procedure pages of the eCRF. If on either of these pages a medication or procedure is reported with the indication 'EFP/cellulite' with a start date prior to the first injection of study drug, then the medication or procedure will be considered a prior EFP treatment.

All medications will be classified as EFP Drug. All procedures will be classified into one of the following groups:

- Liposuction
- Laser
- Massage
- Radiofrequency
- Mesotherapy
- Cream
- Other

The classification will be reviewed and approved by the study medical monitor. Any EFP treatment used after the Day 1 visit will be noted and reported as a protocol violation.

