#### **6.4.1.3. Missing EFP Onset Date**

Missing EFP onset days will be imputed with the first day of the month and missing onset month will be imputed with January. If the EFP onset date is indicated as completely unknown but starting less than 5 years ago, the EFP onset date will be imputed as the informed consent date minus 5 years. If the EFP onset date is indicated as completely unknown but starting more than 5 years ago, the EFP onset date will not be imputed. Missing EFP medication/treatment end days will be imputed with the last day of the month and missing end months will be imputed with December, except if the end year is equal to the date of injection year and then the EFP medication/treatment end date will be imputed with the first injection date.

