#### **7.5. EFP History**

EFP history will be summarized by treatment arm and by treatment region (ie, Buttocks, Thighs, and Overall) using counts and percentages which will include:

- Family history of cellulite (Yes/No)
- Age (years) at EFP symptom onset (summarized descriptively)
- Prior treatments for EFP including liposuction, laser, massage, radiofrequency, drug, mesotherapy, cream, other, or none. Subjects can report more than 1 prior EFP treatment.
- Number of prior EFP treatments (0, 1, 2, or  $\geq 3$ )
- Time (years) since most recent EFP treatment (summarized descriptively)

Refer to [Table 12](#) for computation of “age at EFP onset” and “time since last EFP treatment.” EFP history will be listed.

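### SAP Table 12 reverses the subtraction for time since last EFP treatment, and one end-date imputation rule keeps the value negative after the order is corrected

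*SAP*

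**What the plan says.** SAP 6.3, Table 12, gives two date-difference variables for EFP history. Time since last EFP treatment is "Date of most recent EFP treatment – Date of informed consent/365.25". Age at EFP symptom onset is "Date of EFP symptoms reported – Date of Birth/365.25". SAP 7.5 reports both in years, as descriptive statistics by treatment arm and region.

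SAP 4.4 decides which treatments enter the first variable: a medication or procedure given for cellulite "with a start date prior to the first injection of study drug, then the medication or procedure will be considered a prior EFP treatment". The reference point there is first injection, not consent.

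SAP 6.4.1.3 covers incomplete dates. A missing end day becomes month-end and a missing end month becomes December. If the end year is also the year of injection, "then the EFP medication/treatment end date will be imputed with the first injection date". For symptom onset with a wholly unknown date but flagged as "starting less than 5 years ago, the EFP onset date will be imputed as the informed consent date minus 5 years". Onset flagged as more than 5 years ago is left missing.

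The schedules of events in both documents place screening, where consent is obtained, between Day -21 and Day -1. SAP Table 13 (changes from protocol) says nothing about these variables.

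**The concern.** A time since an event should be the later date minus the earlier one. Table 12 has it the other way round, and the missing brackets hide this, because a programmer who adds them may think the formula is repaired. If the rule is followed, the EFP-history table would show negative years since treatment.

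The end-date exception is a second, independent problem. It places the end of a prior treatment on Day 1, after consent, while the interval is counted back from consent. Correcting the formula alone therefore leaves some negative values.

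At stake are two baseline descriptors. Arms are filled by sequential assignment (protocol 12.4, SAP 3.6.2), with six subjects per region and arm, so a reader of the report may look to the baseline tables to see how alike the arms are.

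**Working it through.** The documents give no numerical result for these variables, so there is no figure to reproduce. The formulas are evaluated on example dates. The dates are assumptions, set around the protocol's estimated first enrolment of September 2018. Dates are expressed as SAS day numbers (days from 1 January 1960), since SAP 6.1 names SAS 9.4.

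- Birth 15 Jun 1978 = 6740
- Symptom onset 15 Jun 2000 = 14776
- Last treatment 31 Mar 2017 = 20909
- Consent 17 Sep 2018 = 21444
- First injection 1 Oct 2018 = 21458

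**Age at symptom onset**

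- Literal operator order: 14776 - 6740/365.25 = 14757.5, which is not in years.
- Brackets added: (14776 - 6740)/365.25 = 8036/365.25 = 22.00 years. Brackets are a complete repair.

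**Time since last treatment**

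- Literal operator order: 20909 - 21444/365.25 = 20850.3, which is not in years.
- Brackets added, order kept: (20909 - 21444)/365.25 = -535/365.25 = -1.46 years.
- Brackets added, order reversed: (21444 - 20909)/365.25 = +1.46 years.

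The negative sign does not depend on the example: treatment date minus consent date is below zero for every treatment that ended before consent.

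**End date set to first injection, with the corrected formula**

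The value is (consent - first injection)/365.25. Consent falls on Day -21 to Day -1, and Table 12 counts pre-treatment study days as a plain difference from Day 1, so the gap is 1 to 21 days.

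- 1 day: -1/365.25 = -0.003 years
- 14 days (example dates): -14/365.25 = -0.038 years
- 21 days: -21/365.25 = -0.057 years

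**Two readings of the exception**

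The sentence in 6.4.1.3 covers missing days and missing months together before stating the exception. If the exception applies to both, a treatment recorded as ending in March 2018 with the day missing becomes 1 October 2018 instead of 31 March 2018. That is 184 days later, and time since treatment becomes -0.04 years instead of 170/365.25 = +0.47. If the exception applies only when the month is missing, no recorded month is overwritten, but the imputed date still falls after consent.

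**Onset flagged as less than 5 years ago**

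With consent on 17 Sep 2018, onset is imputed as 17 Sep 2013. This is the earliest edge of the flagged interval, so any error runs one way: age at onset is understated by between 0 and 5 years.

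**The case against.** Several arguments on the other side have force.

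- **Brackets.** Only the bracketed reading yields years, and SAP 7.5 states years. A reader might infer that ages in the thousands will be reported; the stated unit makes that implausible. If the table is laid out as a fraction in the published SAP, the bracket point falls away altogether. The order of subtraction does not.
- **Sign convention.** Table 12 also makes study days before Day 1 negative, so a negative value could be called deliberate. But this variable is named and reported as time since an event, and the AE duration in the same table runs later minus earlier. This defence does not hold.
- **Purpose of the exception.** Without it, month-end or December imputation in the injection year could place a prior treatment after first injection. Stopping at first injection also matches the definition in SAP 4.4. That is a fair reason for having a limit. The difficulty is that the interval is measured from consent, and the discrepancy is at most about 0.06 years unless a recorded month is overwritten.
- **The 5-year rules.** A reader might infer that the onset imputation contradicts the record. A strict reading of less than 5 years does exclude exactly 5, but only as the boundary of an excluded range. The one 5-year eCRF item described, for medical history in SAP 3.12, is worded as within 5 years, which may include 5. The wording of the EFP item is not shown. The branch for more than 5 years creates no date, so it contradicts nothing. It does leave a selected subset in the mean, but SAP 6.1 footnotes subjects removed from an analysis and SAP 7.5 lists EFP history. Midpoint imputation is an alternative convention, and an average bias of 2.5 years would rest on an assumed uniform distribution.
- **Comparability of arms.** A reader might infer that these errors distort the comparison of non-randomised arms. The SAP does not say these variables will be used for that purpose. The sign and bracket errors also apply equally in every arm: reversal changes the direction of a difference but cannot create one.

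**Conclusion.** The reversed subtraction is a real error in a stated derivation, and nothing elsewhere in the SAP or protocol corrects it. It changes the sign of every value for a treatment that ended before consent, whatever dates are assumed. The missing brackets in both formulas are a notation error.

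The end-date exception is a smaller, separate fault. It gives values between about -0.003 and -0.06 years under the corrected formula. It overwrites a known month only if the exception is read to include missing days, which the text allows but does not settle.

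The documents do not say how many subjects will have prior treatments, incomplete end dates or unknown onset dates, so the effect on any table mean cannot be sized. No efficacy model, safety summary or population definition uses these variables. The consequence is confined to the descriptive EFP-history tables by arm and region. The point is minor and worth correcting because the correction is almost free.

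**What to change.** In SAP Table 12:

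- Time since last EFP treatment = (Date of informed consent - Date of most recent EFP treatment)/365.25.
- Age at EFP symptom onset = (Date of EFP symptom onset - Date of birth)/365.25.

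In SAP 6.4.1.3, replace the injection-year exception. Impute an incomplete treatment end date as the last day of the recorded month, or of December if the month is missing. Limit it to no later than the consent date, but never earlier than the recorded start date. Set time since treatment to zero if the treatment started after consent. The start-date condition is needed because SAP 4.4 admits treatments that began between consent and first injection, and an unconditional limit at consent would end those before they started. Use the limited date only to derive this variable and keep the recorded partial date in the listing.

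Optionally, next to mean age at onset, show how many subjects had an unknown onset date that was imputed and how many had one left missing.

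The cost is about four lines of SAP text and the matching programming. No new data are needed, and no other planned analysis changes.
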